7.11 End of trial

The trial will end 31 days after the last recruited recipient participant receives their transplant. Day 1 will be considered the day that the participant is admitted to ICU following their transplant implantation procedure, with 31 days counted inclusively and the trial ending at 23:59 on the 31st day.

8 TRIAL TREATMENTS

8.1 Name and description of investigational medicinal product(s)

8.1.1 Custodiol-HTK Solution for Cardioplegia Infusion

Custodiol-HTK Solution for Cardioplegia Infusion, also known as Custodiol-HTK and Bretschneider HTK solution is a medicinal solution indicated for Cardioplegia in cardiac surgery operations, protection of organs during operations in a bloodless field (heart, kidney, liver) and preservation of organ transplants (heart, kidney, liver, pancreas).

8.1.2 Sterile Concentrate for Cardioplegia Infusion

Sterile Concentrate for cardioplegia infusion, also known as St Thomas' Solution, is indicated for cardioplegia during cardiac surgery and is used for organ preservation during cardiac transplantation.

8.2 Regulatory status of the drug

8.2.1 Custodiol-HTK Solution for Cardioplegia Infusion

Custodiol-HTK is manufactured and licensed by [name] Köhler Chemie GMBH. Marketing authorisation number: PL 41891/0001

8.2.2 Sterile Concentrate for Cardioplegia Infusion

Macarthy's Laboratories Ltd, trading as Martindale Pharmaceuticals, holds marketing authority for use in the UK. Marketing authorisation number: PL 01883/0012

8.3 Product Characteristics

The simplified IMP dossier will contain the Summary of Medicinal Product Characteristics for Sterile Concentrate for Cardioplegia Infusion and Custodiol-HTK. In the unlikely event that one of these is updated during the trial recruitment period, it will be the responsibility of the CI to circulate updated versions to the PIs in each centre. It would then be the responsibility of each PI to ensure all site files contain only the updated versions.

8.4 Drug storage and supply

All pharmacy aspects of the trial at the participating sites are the responsibility of the PI who will delegate this responsibility to the local pharmacist, or other appropriately qualified personnel. The delegation of duties must be recorded on the Delegation log. The PI or delegated individual must ensure that the IMP are stored in accordance with local practice, applicable regulatory and trial-specific requirements. Refer to the Pharmacy manual for more information.

The site Pharmacy must maintain accountability records as per their site operating procedures for all the IMPs which may include receipt, returned medication, and destruction of returned/unused IMP. The site staff responsible for the storage conditions, temperature excursions, use and transport of the IMP must also maintain accountability logs. Copies of completed IMP accountability logs must be submitted for all trial recipients upon request from the Sponsor for monitoring purposes.

Following the termination of the trial and at the request of the Sponsor, all unused IMPs will be accounted for and destroyed locally at trial sites in accordance with local practice. See the latest version of the Pharmacy manual for details. No IMP is to be returned to either supplier or Sponsor.

F-CUSToS Protocol Version Number 2.0; Dated 30 January 2025

8.4.1 Custodiol-HTK Solution for Cardioplegia Infusion

Custodiol-HTK will be provided free of charge by the supplier (Pharmapal Ltd.). Each centre will receive a shipment at the beginning of the study, which should be sufficient for the duration of the study. In the event that a centre requires additional Custodiol-HTK, the PI in that centre will inform the supplier, who will arrange for additional Custodiol-HTK to be delivered.

Custodiol-HTK must be stored in a refrigerator at $2^{\circ}\text{C} - 8^{\circ}\text{C}$ and protected from light exposure. Custodiol-HTK must be stored in an insulated cool box with ice during transport to the organ retrieval site. It has a shelf life of one year. Once opened it must be used or discarded.

8.4.2 Sterile Concentrate for Cardioplegia Infusion

St Thomas' Solution will be procured by the local pharmacy at each site at market price, as would occur normally for a cardiac transplant to occur in the UK. Each site routinely maintains an adequate supply of St Thomas' solution to ensure that cardiac organ retrieval can occur.

St Thomas' solution should be stored below 25°C and protected from light exposure. It has a shelf life of three years. Once opened it must be used or discarded.

8.5 Preparation and labelling of Investigational Medicinal Product

8.5.1 Custodiol-HTK Solution for Cardioplegia Infusion

Custodiol-HTK comes in a ready-to-use form and will be prepared and labelled in accordance with its current marketing authorisation, with no changes as a result of this trial.

8.5.2 Sterile Concentrate for Cardioplegia Infusion

The contents of one (20 ml) ampoule of St Thomas' solution must be diluted with 1 litre of Compound Sodium Chloride Injection BPC, immediately before use. The product will be labelled in accordance with its current marketing authorisation, with no changes as a result of this trial.

8.6 Dosage schedules

Organ retrieval proceeds according to a nationally standardised Protocol, as set by the National Organ Retrieval Service. The only change to this Protocol will be the following:

8.6.1 Custodiol-HTK Solution for Cardioplegia Infusion

Following cross-clamping of the ascending aorta, at least 3.5L of cold Custodiol-HTK will be perfused into the aortic root, over at least 10 minutes.

Perfusion technique:

After clamping the aorta and simultaneous "venting" of the left ventricle, the solution will be administered antegrade. Cardioplegic perfusion can be performed by either a roller pump with constant volume or by gravity (after cardiac arrest, the solution bag must be kept at 60 cm water column above the level of the heart, which is equivalent to a perfusion pressure of 40-50mm Hg).

Storage of donor heart for transport:

F-CUSToS Protocol Version Number 2.0; Dated 30 January 2025

- 1. Inner bag: 2L of cold Custodiol-HTK $(2^{\circ}C 4^{\circ}C)$
- 2. 2nd bag: 2L of cold saline $(2^{\circ}C 4^{\circ}C)$
- 3. Outer bag: 2L of cold saline $(2^{\circ}C 4^{\circ}C)$

This is a minor alteration to the method of administration laid out in the SmPC. The alteration has been discussed with and approved by the makers of Custodiol-HTK Solution and is based on a proven and successful Protocol for use in cardiac transplantation. It has also been discussed with and agreed upon by all the PIs.

8.6.2 Sterile Concentrate for Cardioplegia Infusion

Sterile Concentrate for Cardioplegia Infusion (SCfCI) will be diluted by adding 20ml of SCfCI to 1 litre of Ringers solution.

Following cross-clamping of the ascending aorta, the correct volume of reconstituted SCfCI will be perfused into the aortic root according to the donor weight as outlined below:

- 3. Donor weight 30-70 Kg: administer 1 litre of reconstituted SCfCI solution
- 4. Donor weight >70 Kg: administer 1.5 L of reconstituted SCfCI solution
- 5. At the request of the recipient transplant surgeon, it is permissible to change the above doses dependent on logistics and/or donor physiology.

Delivery pressure: 60-90 mmHg

Storage of donor heart for transport:

- 4. Inner bag: 2L of cold saline $(2^{\circ}C 4^{\circ}C)$
- 5. 2nd bag: 2L of cold saline $(2^{\circ}C 4^{\circ}C)$
- 6. Outer bag: 2L of cold saline $(2^{\circ}C 4^{\circ}C)$

This method of administration is in accordance with the NORS Protocol. The SmPC for Sterile Concentrate for Cardioplegia Infusion does not state doses, delivery pressure or temperature for administration in cardiac transplantation.

8.7 Dosage modifications

Repeat doses may be given of either drug according to surgeon and perfusionist preference in the event that electromechanical cardiac arrest is not achieved or sustained with the initial dose.

8.8 Transport of treatments to retrieval site

Each NORS team will be required to transport both solutions with them to the donor site.

The NORS team should carry at least 6L of Custodiol-HTK to the donor hospital. This should be stored in a cool box with ice and protected from light exposure. Custodiol-HTK will be provided in the form of 2L bags.

The NORS team should carry at least five 20 ml ampoules of Sterile Concentrate for Cardioplegia Infusion and 5L of Compound Sodium Chloride Injection BPC. This can be stored at room temperature and should be protected from light exposure.

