8.13 Assessment of compliance with treatment

Compliance will be assessed by each PI and the Sponsor. Each randomised case will be reviewed for compliance with the randomisation procedure, treatment allocation and treatment dosage, in accordance with the primary outcome of the trial.

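### The 6 L minimum of Custodiol-HTK in section 8.8 leaves 0 to 0.5 L for the repeat dose that section 8.7 permits, if the heart is still to be stored in 2 L of the solution

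*Protocol*

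**What the plan says.** Four parts of the Protocol bear on how much Custodiol-HTK is needed at the donor hospital.

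- **Perfusion (8.6.1).** After cross-clamping, "at least 3.5L of cold Custodiol-HTK will be perfused into the aortic root, over at least 10 minutes". No upper limit is given.
- **Storage (8.6.1).** The innermost transport bag is specified as "Inner bag: 2L of cold Custodiol-HTK". No other storage fluid is named for this arm.
- **Repeat dosing (8.7).** "Repeat doses may be given of either drug according to surgeon and perfusionist preference", where the first dose does not achieve or sustain arrest. Neither a volume nor a maximum number is stated.
- **Stock carried (8.8).** "The NORS team should carry at least 6L of Custodiol-HTK to the donor hospital", and "Custodiol-HTK will be provided in the form of 2L bags".

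For St Thomas' solution, section 8.8 asks for at least five 20 ml ampoules and 5 L of diluent. Section 8.6.2 sets a dose of 1 L or 1.5 L by donor weight and stores the heart in saline.

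**The concern.** The minimum in 8.8 fits the regimen in 8.6.1 but makes almost no allowance for the contingency in 8.7. A team that complies exactly with 8.8 and then needs a repeat of more than 0.5 L has three choices. It can forgo the repeat, use the other solution, or draw on the bag meant for storage and transport the heart in less than 2 L of Custodiol-HTK or in some other fluid.

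The shortage cannot be made good on the day. Under section 7.3 randomisation happens once the retrieval operation is under way, so the team has only what it brought. The resupply route in 8.4.1 ("In the event that a centre requires additional Custodiol-HTK, the PI in that centre will inform the supplier") replenishes a centre's stock and does not reach a team in theatre elsewhere.

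What is at stake is the protection of the donor heart and clean delivery of the allocated regimen, in one arm only. Section 8.13 states: "Each randomised case will be reviewed for compliance with the randomisation procedure, treatment allocation and treatment dosage, in accordance with the primary outcome". Use of the other solution or an altered storage regimen would therefore come up at that review. The Protocol does not say whether either would fail component (iii) of the primary endpoint in section 3.3.1, which concerns preservation in the allocated solution.

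**Working it through.** This is volume arithmetic.

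**Inputs.** Perfusion of at least 3.5 L and storage of 2 L (8.6.1); bag size 2 L and minimum carried 6 L (8.8). The repeat volume *r* is not given in 8.7. It is treated as an assumption and shown from 0.5 L up to a full 3.5 L.

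**Step 1: reproduce the stated minimum.** 3.5 + 2 = 5.5 L; 5.5 / 2 = 2.75, rounded up to 3 bags = 6 L. The figure in 8.8 is correct for the regimen without a repeat.

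**Step 2: spare volume at the minimum, with 2 L kept for storage.**

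- After a 3.5 L dose: 6 − 3.5 − 2 = 0.5 L.
- After both perfusion bags are run through (4 L, which 8.6.1 allows): 6 − 4 − 2 = 0 L.

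**Step 3: volume left for storage at 6 L after a repeat, and bags needed to keep the full 2 L.** Left for storage = 6 − first dose − *r*. Bags = (first dose + 2 + *r*) / 2, rounded up.

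| Repeat *r* (assumed) | Left for storage, first dose 3.5 L | Bags needed | Left for storage, first dose 4 L | Bags needed |
|---|---|---|---|---|
| 0.5 L | 2.0 L | 3 | 1.5 L | 4 |
| 1 L | 1.5 L | 4 | 1.0 L | 4 |
| 1.5 L | 1.0 L | 4 | 0.5 L | 4 |
| 2 L | 0.5 L | 4 | 0 L | 4 |
| 2.5 L | 0 L | 4 | 0.5 L short | 5 |
| 3.5 L | 1 L short | 5 | 1.5 L short | 5 |

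In the cells marked short, the repeat itself cannot be completed, even with nothing kept for storage.

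**Step 4: what larger minimums cover, with 2 L kept for storage.**

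- 8 L (four bags): 8 − 3.5 − 2 = 2.5 L, or 8 − 4 − 2 = 2 L, for a repeat. This covers a partial repeat only.
- 10 L (five bags): a full repeat needs 3.5 + 3.5 + 2 = 9 L, or 4 + 3.5 + 2 = 9.5 L after a 4 L first dose. Both fit.

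**Step 5: the other arm.** Five ampoules, each in 1 L, give about 5 L. Spare after one dose is 5 − 1 = 4 L or 5 − 1.5 = 3.5 L, enough for 4 / 1 = 4 or 3.5 / 1.5 = 2.3 full repeats. None is used for storage.

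**The case against.** The strongest reply is that nothing here is stated wrongly. Six litres is a minimum and a team may take a fourth bag. Section 8.7 grants a permission and fixes no quantity, so the two sections can both stand, and a top-up of 0.5 L after a 3.5 L dose fits. That is right. A reader might infer that the 6 L figure is miscalculated or that 8.7 and 8.8 flatly contradict each other, but step 1 reproduces the figure and the documents do not support either reading. What remains is that a team fully compliant with 8.8 may be unable to use 8.7 beyond 0.5 L and still follow 8.6.1.

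The second reply is rarity. The shortfall needs a team at the minimum, arrest not achieved or sustained after at least 3.5 L, and a repeat above the spare volume. The Protocol gives no frequency for these, and its Background section says the effect of Custodiol-HTK outlasts 2 hours in routine cardiac surgery. This stands and limits the weight of the point.

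Third, a reader might infer that such cases would lower the primary proportion. The documents do not show that. A heart kept in 1 to 1.5 L of Custodiol-HTK is arguably still preserved in its allocated solution, and the Protocol does not rule on it.

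Finally, the Pharmacy manual or the national retrieval protocol, neither shown, might specify a reserve. That is possible, but 8.8 itself fixes a figure and should agree with 8.7.

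**Conclusion.** The point holds as a minor mismatch in the supply specification. At the 6 L minimum, 0 to 0.5 L of Custodiol-HTK is available for a repeat dose if 2 L is kept for storage. The St Thomas' arm has 3.5 to 4 L available for the same purpose. The mismatch affects only teams carrying no more than the minimum, and only when a repeat larger than the spare is wanted.

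The spare volumes follow directly from the Protocol. The 0 L end supposes that 4 L is perfused, and all repeat volumes are assumptions. The number of hearts affected cannot be estimated from the document, and no effect on the primary proportion or on the decision to proceed to the main trial is claimed.

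**What to change.** Raise the minimum in section 8.8 to at least 8 L (four 2 L bags), and state that this covers a partial repeat of up to 2.5 L after a 3.5 L first dose, or 2 L after 4 L, with 2 L kept for storage. If section 8.7 is meant to allow the full 3.5 L to be repeated, set the minimum at 10 L (five bags). Section 8.7 should say which is intended. The Pharmacy manual should be checked so that it matches.

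Keeping 6 L and reserving 2 L for storage before any repeat is not a good substitute. It would restrict a rescue dose to 0 to 0.5 L in a heart that has not arrested.

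**Cost.** One figure in 8.8 and a clarifying sentence, plus one or two more bags in the cool box at each retrieval, often unused. Over the 50 planned hearts that is 50 bags (50 × 2 = 100 L) at 8 L, or 100 bags (200 L) at 10 L, plus those taken to retrievals that are not randomised. On price, "Custodiol-HTK will be provided free of charge by the supplier". Section 8.4.1 requires only opened product to be used or discarded. The Protocol does not say whether unopened bags return to stock, so extra consumption over the 50 hearts lies between 0 and 50 bags, or 0 and 100. Cool-box capacity is not given and should be confirmed with the retrieval teams.

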8.9 Heart for Valves/Research

In the unlikely event that a heart randomised to receive Custodiol-HTK is deemed not transplantable after delivery of Custodiol-HTK, this heart may be offered on to another recipient via the ODT Hub. Any accepting team would need to be informed that the heart was preserved in Custodiol-HTK and factor this into their decision-making. If the heart is not accepted after offering on, the heart may not be used for valves. Hearts for valves, according to current NHSBT protocols, must be preserved with St Thomas' solution. Where the heart is not suitable to be used for valves, it may be offered to other research projects, providing they are informed that the heart is preserved in Custodiol-HTK.

8.10 Known drug reactions and interaction with other therapies

There are no known drug reactions or interactions with other therapies for either IMP.

8.11 Concomitant medication

Any concomitant medication will be decided by the physicians caring for the transplant recipient and organ donor. No modifications to these should be made as a result of participation in this trial.

8.12 Trial restrictions

There are no trial restrictions. The aim is to exactly replicate the real-world scenario in cardiac transplantation, only altering the myocardial preservative solution.

8.13 Assessment of compliance with treatment

Compliance will be assessed by each PI and the Sponsor. Each randomised case will be reviewed for compliance with the randomisation procedure, treatment allocation and treatment dosage, in accordance with the primary outcome of the trial.

9 PHARMACOVIGILANCE

9.1 Definitions

Term	Definition					
Adverse Event (AE)	Any untoward medical occurrence in a participant to whom a medicinal					
	product has been administered, including occurrences which are not					
	necessarily caused by or related to that product.					
Adverse Reaction	An untoward and unintended response in a participant to an investigational					
(AR)	medicinal product which is related to any dose administered to that					
	participant. The physics "manning to an investigational medicinal product" means that					
	The phrase "response to an investigational medicinal product" means that a causal relationship between a trial medication and an AE is at least a					
	reasonable possibility, i.e., the relationship cannot be ruled out.					
	All cases judged by either the reporting medically qualified professional or					
	the Sponsor as having a reasonable suspected causal relationship to the trial					
	medication qualify as adverse reactions. It is important to note that this is					
	entirely separate to the known side effects listed in the SmPC. It is					
	specifically a temporal relationship between taking the drug, the half-life,					
	and the time of the event or any valid alternative aetiology that would					
	explain the event.					
Serious Adverse Event	A serious adverse event is any untoward medical occurrence that:					
(SAE)	• results in death					
	• is life-threatening					
	requires inpatient hospitalisation or prolongation of existing					
	hospitalisation					
	results in persistent or significant disability/incapacity					
	consists of a congenital anomaly or birth defect					
	Other 'important medical events' may also be considered serious if they					
	jeopardise the participant or require an intervention to prevent one of the					
	above consequences.					
	NOTE: The term "life-threatening" in the definition of "serious" refers to					
	an event in which the participant was at risk of death at the time of the					
	event; it does not refer to an event which hypothetically might have caused					
Serious Adverse	death if it were more severe. An adverse event that is both serious and, in the opinion of the reporting					
Reaction (SAR)	Investigator, believed with reasonable probability to be due to one of the					
Macdon (Dill)	trial treatments, based on the information provided.					
Suspected Unexpected	A serious adverse reaction, the nature and severity of which is not					
Serious Adverse	consistent with the information about the medicinal product in question set					
Reaction (SUSAR)	out in the reference safety information:					
	• in the case of a product with a marketing authorisation, this could be					
	in the summary of product characteristics (SmPC) for that product, so					
	long as it is being used within its licence. If it is being used off label					
	an assessment of the SmPCs suitability will need to be undertaken.					
	• in the case of any other investigational medicinal product, in the					
	investigator's brochure (IB) relating to the trial in question					

NB: to avoid confusion or misunderstanding of the difference between the terms "serious" and "severe", the following note of clarification is provided: "Severe" is often used to describe intensity of a specific event, which may be of relatively minor medical significance. "Seriousness" is the regulatory definition supplied above.

Detailed guidance can be found here:

http://ec.europa.eu/health/files/eudralex/vol-10/2011_c172_01/2011_c172_01_en.pdf

Refer to the SAE Guidelines for Sites for more information.

9.2 Operational definitions for (S)AEs

The operational definition for SAEs will be any adverse event (as defined above in 9.1) that occurs from the time of perfusion of the treatment into the aortic root until 24 hours post-transplant (the longest timeframe which can reasonably be attributed to have any relationship to the treatment, as the treatment is entirely washed out on reperfusion of the heart) and is not included in the below list of expected possible complications from undergoing cardiac transplantation:

- i. Primary Graft Dysfunction
- ii. The use of mechanical circulatory support, including intra-aortic balloon pump
- iii. The need for renal replacement therapy
- iv. The use of vasoactive inotrope medication
- v. The ongoing need for prolonged invasive mechanical ventilation
- vi. Infection requiring antibiotic treatment
- vii. Return to theatre for bleeding, instigation or removal of mechanical circulatory support, chest opening or chest closure
- viii. The need for blood or blood product transfusion
 - ix. The need for temporary or permanent cardiac pacing
 - x. Stroke
 - xi. Myocardial Infarction
- xii. Acute or Hyperacute Allograft Rejection
- xiii. Venous Thromboembolism
- xiv. Aortic dissection
- xv. The use of immunosuppression including pulsed steroids and biologic agents
- xvi. The need for re-transplant
- xvii. The need for further invasive procedures such as coronary angiography, plastic surgery, interventional radiology, vascular surgery, abdominal surgery or placement of intrathoracic or intra-abdominal drains

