Early cessation would be considered if there was a 30% absolute risk reduction in primary graft dysfunction in one treatment arm, as this is the point at which there would be sufficient power to confidently confirm that one arm reduced primary graft dysfunction with a 5% significance level at 80% power. Early cessation will also be considered where the DSMC has concerns that one treatment leads to a significant increase in SARs and/or SAEs.

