9.3 Recording and reporting of SAEs, SARs AND SUSARs

All SAEs/SARs/SUSARs occurring from the time of perfusion of the treatment into the aortic root until 24 hours post-transplant must be recorded on the electronic AE Form **within 24 hours** of the research staff becoming aware of the event. NB 24 hours post has been chosen because all the IMP is washed out on reperfusion of the heart and cannot reasonably be expected to still be present or have any direct effect beyond 24 hours. "Post-transplant" will be defined as the time the recipient leaves the operating theatre after they receive their transplant or death where this

occurs during the transplant implantation. Death during the implantation would be considered a SAE and should be recorded as such, with the PI review of expectedness in relation to the IMP.

For each SAE/SAR/SUSAR the following information will be collected:

- i. full details in medical terms and case description
- ii. event duration (start and end dates, if applicable)
- iii. action taken
- iv. outcome
- v. seriousness criteria
- vi. causality (i.e., relatedness to trial drug / investigation), in the opinion of the investigator
- vii. whether the event would be considered anticipated.

Any change of condition or other follow-up information should be emailed to the Sponsor as soon as it is available or at least within 24 hours of the information becoming available. Events will be followed up until the event has resolved or a final outcome has been reached.

For any other complication, not listed above in section 9.2, occurring within 24 hours of the transplant implantation the information listed above must be collected. However, it will then be the responsibility of the PI to determine whether or not this is likely to be related to the IMP-treatment. If it is deemed likely to be related it will be termed an AR. The PI will also have responsibility for determining the level of seriousness, according to definitions outlined in section 9.1. If an AE/AR is assigned by the PI or delegate (or following central review) as serious it will be termed and SAE/SAR. As there is no reference safety information for either treatment in the trial, all SARs will automatically be treated as SUSARs and will be subject to expedited reporting to the Medicines and Healthcare Products Regulatory Agency (MHRA). The sponsor will inform the MHRA, the REC and Marketing Authorisation Holder of SUSARs within the required expedited reporting timescales.

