16.2 Appendix 2 – Schedule of Procedures

Procedures			Visits					
	Recipient Screening	Donor Screening	Recipient Pre-Op Clinic	Recipient Pre-Op	Donation	Implantation	24-hour follow-up	30-day Follow Up
Eligibility Screening	Х	х						
PIS sent by letter	Х							
Provide information on the purpose of the trial			X					
Informed consent discussion			X					
Informed consent confirmation				X				
Demographics			X		X			
Baseline Data			X		X (donor)			
Randomisation					X			
Treatment					X			
Intra-op TOE						X		
Post-op Right Heart Catheter							X	
Post-op Blood tests (U&E)							Х	
30-day follow- up data								X
Adverse event assessments						X	X	X
Physician's Withdrawal						X	X	X
Checklist								

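### Sections 9.1, 9.2 and 9.3 define an SAE in conflicting ways, and the 9.2 list keeps serious events such as stroke and re-transplant out of the count that 7.10 relies on

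*Protocol*

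**What the plan says.** - **Section 9.1** has a broad adverse event entry ("including occurrences which are not" attributable to the product) and a narrower one for SAEs: "A serious adverse event is any untoward medical occurrence that" meets one of the usual criteria, such as death, threat to life or prolonged hospitalisation.
- **Section 9.2** sets the operational rule: "The operational definition for SAEs will be any adverse event (as defined above in 9.1"), from aortic root perfusion to 24 hours post-transplant, provided that the event "is not included in the below list of expected possible complications from undergoing cardiac transplantation". The list has items i to xvii. Among them are stroke (x), myocardial infarction (xi), acute or hyperacute rejection (xii), aortic dissection (xiv) and "The need for re-transplant" (xvi).
- **Section 9.3** uses the same window: "All SAEs/SARs/SUSARs occurring from the time of perfusion of the treatment into the aortic root until 24 hours post-transplant must be recorded". For complications that are not on the 9.2 list, the PI judges relatedness and then seriousness by the 9.1 criteria, and only events graded serious become SAEs or SARs. Death during implantation is named as an SAE.
- **Section 7.10** has early cessation considered where the DSMC is concerned that "one treatment leads to a significant increase in SARs and/or SAEs". Separately, a primary graft dysfunction (PGD) rate above 50% or 30-day survival below 88.8% counts as a DSMC concern, and a 30% absolute difference in PGD is its own ground for early cessation.

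**The concern.** An SAE count is only useful to a monitoring committee if every site builds it in the same way and it contains the serious events. Here six centres can apply 9.2 or 9.3 and obtain different counts from the same patients. Whichever they apply, the listed complications drop out regardless of severity.

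The list describes what is expected after a heart transplant, not what is expected from the preservation solution. A difference between arms in such events is what a DSMC would want to see, because randomisation makes the background risk of the operation alike in both arms. If the list removes the events before they are graded, an imbalance in stroke, infarction or early graft loss cannot show in the count that 7.10 points to.

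Re-transplant raises a further point. Sections 6.1 and 6.2 foresee emergency re-transplant in the same admission and keep the index transplant in the trial, yet no outcome or listed form item records that it happened.

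**Working it through.** The protocol states no figure on this point to reproduce. The check sets the sections against each other, counts the list, and then looks at scale.

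**1. The same event under each section**

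| Event | 9.1 | 9.2 | 9.3 |
|---|---|---|---|
| Minor, unlisted, inside the window | AE, not SAE | SAE | Not SAE once the PI grades it non-serious |
| Serious, unlisted, inside the window | SAE | SAE | SAE |
| Life-threatening, non-fatal stroke inside the window | SAE | Not SAE (item x) | Outside the PI step; no assessment asked for |
| Re-transplant inside the window | SAE where a criterion is met | Not SAE (item xvi) | Outside the PI step; no assessment asked for |
| Re-transplant after the window | SAE where a criterion is met | Not SAE (window and list) | Not SAE (window) |

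Row 1 is a conflict between 9.2 and 9.3. Rows 3 and 4 are a conflict between 9.1 and 9.2 that 9.3 does not repair. In row 5 the window alone excludes the event, so changing the list would not capture it; only a form field would.

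**2. The list against the data items in section 7.7**

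- Recorded there: PGD, mechanical support, renal replacement, inotropes, infection, stroke, infarction, rejection and thromboembolism, which makes 9.
- Not recorded as an item: prolonged ventilation, return to theatre, transfusion, pacing, aortic dissection, immunosuppression, re-transplant and further invasive procedures, which makes 17 − 9 = 8.

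Stroke, infarction and rejection are yes/no items at 30 days, with no seriousness or relatedness field listed. For graft and patient outcome at 30 days the form asks only alive or dead. The trial closure call in 7.8 adds survival status, time and cause of death, and length of stay, but not re-transplant.

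**3. Scale**

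At the 36% PGD rate in 7.10, 0.36 × 50 = 18 participants, or about 9 per arm at 25 each, would have an event that item i alone keeps out of the SAE count.

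Section 7.10 does not define a significant increase. Suppose, as an assumption, a two-sided Fisher exact test at 5% with 25 per arm.

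- 0 v 5 participants: p = 2 × C(25,5)/C(50,5) = 2 × 53,130/2,118,760 = 0.0502, not significant.
- 0 v 6: p = 2 × C(25,6)/C(50,6) = 2 × 177,100/15,890,700 = 0.022, significant.
- The next smallest significant splits are 1 v 7, 2 v 9 and 3 v 11.

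So even 6 v 0 in, say, strokes and infarctions inside the window would be significant on this test but would enter the SAE count as 0 v 0. Under the literal 9.2 wording, six participants with minor unlisted events in one arm would count in full.

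**The case against.** Much of the case on the other side stands, and it limits the point.

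- **A reader might infer that trivial events are counted as SAEs.** Section 9.3 has the PI grade seriousness and section 9.4 repeats that duty, so this is a drafting conflict, not a settled rule. Section 9.4 is general, however, and does not bring listed events back into the SAE definition.
- **A reader might infer that all 17 items are serious.** They are not. Inotropes, transfusion, temporary pacing and immunosuppression are treatments or expected care.
- **A reader might infer that the SAE count fails to measure serious harm.** Unlisted serious events and implantation deaths count. Section 9.5 sends every death to the sponsor with a judgement of relatedness, so a fatal listed event is assessed. PGD, the main harm expected from poor preservation, has its own triggers, and with about 18 cases expected there is good reason to keep it out of an SAE tally.
- **A reader might infer a formal SAE stopping comparison.** Section 7.10 only has early cessation considered on DSMC concern, with no test or threshold, and 9.4 has the DSMC review overall safety data.
- **A reader might take the 30-day entry for "Adverse event assessments" in Appendix 2 as a second, conflicting window.** It can be read as follow-up of events that began within 24 hours, which 9.3 and 9.9 require.
- **Some of the eight unrecorded items are partly captured,** for example through the free-text rhythm item, length of ICU stay or the mechanical support item. NHSBT registry data may show a re-transplant, but the protocol does not name it as an item to extract.

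Exempting expected complications from rapid individual reporting is a reasonable choice. None of these points supplies a seriousness or causality judgement for a non-fatal listed event.

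**Conclusion.** The point holds in limited form. Sections 9.1, 9.2 and 9.3 cannot all be followed, and 9.2 is the outlier because it omits the criterion that 9.1 sets and 9.3 applies. The list takes serious non-fatal events, notably stroke, myocardial infarction, aortic dissection, hyperacute rejection and re-transplant, out of SAE status whatever their severity. They are then absent from the SAE/SAR count named in 7.10 and have no DSMC trigger of their own. Eight of the 17 items have no direct item in 7.7. Re-transplant matters most of these, because survival on a second graft is recorded only as survival.

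This rests on the protocol text alone. The SAE guidelines for sites, the trial monitoring plan, the DSMC terms of reference and the registry extract are cited but not shown, and they may narrow the gap in practice. The Fisher figures illustrate scale under an assumed test; the protocol does not prescribe one.

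**What to change.** 1. In 9.2, define an SAE as an adverse event in the stated window that meets at least one 9.1 seriousness criterion, so that 9.1, 9.2 and 9.3 agree.
2. Keep the 17-item list, but only as an exemption from individual 24-hour SAE reporting.
3. In 9.3, require a causality judgement for any listed event that meets a 9.1 criterion. An event judged related then follows the SAR route that 9.3 already sets.
4. Tabulate serious listed events by arm for the DSMC, beside the SAE/SAR table.
5. Add to the 30-day form in 7.7: re-transplant yes/no, with date.

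The cost is slightly more assessment at sites, one extra form field and a longer DSMC table. Neither the sample size nor the primary outcome changes.
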